
Safety Monitoring
	
The safety profiles for CMB305 and atezolizumab are described in their respective Investigator’s Brochures (IBs). Safety will be monitored by evaluating solicited and spontaneously reported adverse events (AEs), including reactogenicity, symptoms, physical examination findings, vital signs, laboratory findings, and discontinuations for AEs. AE severity assessments will be performed using National Cancer Institute (NCI) Common Terminology Criteria for Adverse Events (CTCAE) v4.03. All adverse events, regardless of relationship to study drug, should be reported until 30 days after the last dose of study drug or until initiation of another anti-cancer therapy, whichever occurs first.
 
AEs (both non-serious and serious) associated with exposure to the study drugs may represent an immunologic etiology. These AEs may occur shortly after the first dose or several months after the last dose of treatment. The study drugs must be withheld for drug-related toxicities as outlined in Appendix F, as well as severe or life-threatening AEs.
 
Data Monitoring Committee
 
A DMC will operate in accordance with a signed charter and will consist of 2 experienced oncologists familiar with clinical use of the study drugs and an ad hoc biostatistician who is knowledgeable about statistical methods for clinical trials and sequential analysis of trial data. The DMC will review all cumulative safety information from the Safety Run-in prior to recommendations for further patient enrollment. Thereafter, the DMC will provide independent review of all safety data every 3 months to minimize risks to study patients. All DLTs and SAEs considered at least possibly related to study regimen will be reviewed by the DMC and the Sponsor as they are reported and on an ongoing basis. These reviews may lead to modification or stopping of the treatment program if related, treatment-emergent adverse events indicate a safety profile that is inconsistent or significantly worse than reported with the use of either CMB305 or atezolizumab

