5.4.2 Dose-Limiting Toxicities

AE severity assessments will be performed using NCI Common Terminology Criteria for Adverse Events (CTCAE) v4.03. Unacceptable toxicity is defined when one third or more of the subjects treated with the combined regimen develop an AE considered Grade 3 or higher and considered at least possibly related to CMB305 or atezolizumab with the exceptions below. Hospitalizations primarily intended to expedite diagnostic evaluations or for elective surgery will not be considered as serious adverse events (SAEs) for the purpose of ascertaining DLT.

Any treatment emergent grade 3 or higher AE that occurs in the DLT assessment window, which is the first 42 days after initiation of study drug, that is deemed possibly, probably or definitely related to the combination of CMB305 and atezolizumab will be considered DLTs with the following exceptions:

- Alopecia or vomiting (unless not controlled by optimal anti-emetics)
- Hepatic enzyme elevations associated with the baseline Grade 2 abnormalities that are noted as exceptions above
- Grade 3 laboratory AEs that are asymptomatic and return to baseline or to Grade 1 within 3 days, unless identified specifically as DLT by the investigator or the Data Monitoring Committee (DMC)
- Grade 3 fatigue
- Grade 3 systemic reactions (such as fever, headache, influenza like symptoms, myalgia, malaise, or nausea) that return to baseline or Grade 1 within 3 days of study inoculation

Atezolizumab has a recognized safety profile. AEs in the combined treatment arm that are attributed to atezolizumab will be evaluated by the DMC and sponsor, but will not be immediately considered as DLTs except as noted ([Section 5.4.3](#)). All DLTs should be reported to the Sponsor in an expedited manner (within 24 hours) and will be reviewed by the DMC. Although these events will not contribute automatically to the DLT stopping criteria, these reviews may lead to modification or stopping of the treatment program if related, treatment-emergent AEs indicate a safety profile that is inconsistent or significantly worse than reported with the use of atezolizumab alone.

During the safety run-in, the following patients will not be considered evaluable for DLTs and will be replaced:

- Patients who withdraw or are withdrawn for either study treatment prior to completing the DLT assessment window for any reason other than a DLT

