5.5 Study Stopping Rule

The preliminary safety of the individual components of CMB305 (LV305 and G305) have been studied in separate Phase 1 studies; however, the safety of the CMB305/atezolizumab combination will be investigated during the 6-12 patient Safety Run-in. The safety profile of CMB305 is discussed in the IB.⁶ Dosing will be suspended in this study if DLT is observed in one third or more patients on the combined regimen (assuming a minimum of 12 combined regimen patients were enrolled at that point and would represent the initial denominator), pending review and recommendation from the DMC.

The Sponsor may also choose to terminate this study at any time. Investigators will be notified if the study is placed on hold, completed, or closed.

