5.6 Dosing Delays/Dose Modifications

There are no adjustments for dose delays for a given patient. Treatment delays of >14 days from the treatment plan for CMB305 components prior to Visit 12 are not permitted. If a patient experiences a DLT during the study, their treatment will be suspended. Further treatment of this patient with LV305, G305, or atezolizumab will be made on a case-by-case basis following evaluation of the risks/benefits by the Investigator and Medical Monitor in consultation with the DMC.

Dosing interruptions are permitted in the case of medical/surgical events or logistical reasons not related to study therapy (e.g., elective surgery, unrelated medical events, patient vacation, and/or holidays). Patients should resume study therapy within 3 weeks of the scheduled interruption, unless otherwise discussed with the Sponsor. The reason for the interruption should be documented in the patient's study record. Further details regarding dosing delays and modifications are provided in [Section 7.2.2](#).

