7.2.2 Dose Modification Guidelines

Dosing interruptions are permitted in case of medical/surgical events or logistical reasons not related to study therapy (e.g., elective surgery, unrelated medical events, patient vacation, and/or holidays). Patients should be placed back on study therapy within 3 weeks of scheduled interruption, unless otherwise discussed with Sponsor. The reason for interruption should be documented in the patient's study records.

There are no adjustments for dose delay for a given patient, and treatment delays for the CMB305 components that are >14 days from the treatment plan before Visit 12 will not be allowed. During the study, if a patient experiences a DLT, treatment of that patient will be suspended. A patient may be considered for receiving further injections of the LV305, G305, or atezolizumab investigational drug product on a case-by-case basis following evaluation of the benefit/risk ratio to the patient by the Investigator and Medical Monitor, in consultation with the

independent DMC (e.g., for patients who have experienced a tumor response and had a non-life- and non-organ-threatening DLT, continuation of treatment as per protocol may be considered).

No reduction or modification of the atezolizumab dose will be allowed. Any toxicities associated or possibly associated with atezolizumab treatment should be managed according to standard medical practice. Additional tests, such as autoimmune serology or biopsies, may be used to determine a possible immunogenic etiology. As a result, study treatment must be withheld for AEs or infusions reactions associated with atezolizumab treatment as outlined in [Appendix F](#).

While most irAEs observed with immunomodulatory agents have been mild and self-limiting, such events should be recognized early and treated promptly to avoid potential major complications. The primary approach to Grade 1-2 irAEs is supportive and symptomatic care; for higher grade irAEs, steroids by mouth or parenterally are given, and either skipping a dose or stopping therapy is appropriate. Recurrent Grade 2 irAEs may also mandate skipping a dose of atezolizumab or the use of steroids as outlined in [Appendix F](#).

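### As DLT is defined (first 42 days), the one-third study suspension rule cannot count later related Grade 3+ events, so it does not match the protocol's own definition of unacceptable toxicity

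*Protocol*

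**What the plan says.** Protocol 5.4.2 contains two toxicity definitions.

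- Its first paragraph has no time limit: "Unacceptable toxicity is defined when one third or more of the subjects treated with the combined regimen develop an AE considered Grade 3 or higher", at least possibly related to CMB305 or atezolizumab, with listed exceptions.
- Its second paragraph defines the DLT itself and ties it to a window: "Any treatment emergent grade 3 or higher AE that occurs in the DLT assessment window, which is the first 42 days after initiation of study" treatment. The synopsis says the same. Neither document gives another definition for later use.

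Three rules then use the bare term DLT.

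- 5.5 (also the synopsis, Safety Monitoring, and the Study Stopping Rule in SAP 3.1): "Dosing will be suspended in this study if DLT is observed in one third or more patients on the combined regimen", pending DMC review, "assuming a minimum of 12 combined regimen patients were enrolled at that point and would represent the initial denominator".
- 5.6: "If a patient experiences a DLT during the study, their treatment will be suspended".
- 7.2.2: "During the study, if a patient experiences a DLT, treatment of that patient will be suspended".

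Two other places bear on timing. The synopsis says of adverse events with a possible immunologic cause: "These AEs may occur shortly after the first dose or several months after the last dose of treatment". Section 9.4.8 lists DLTs among the medical events of interest (MEOIs). These are reportable up to 90 days after treatment ends, or 30 days after a new anticancer therapy starts if that is earlier.

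**The concern.** A 42-day window suits a 3+3 run-in. The difficulty is that the same word then drives rules that are meant to work for the whole study. The run-in has 3 to 6 combination patients, unless a dose reduction adds more. A rule whose first denominator is 12 is plainly meant for the main study.

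Read literally, 5.5 never counts a related Grade 3 or higher event that starts after Day 42. The combination could therefore meet the protocol's own description of unacceptable toxicity without reaching the suspension rule that carries the same one-third threshold. Read by intent, with the study-long phrasing in 5.6 and 7.2.2 and the reporting period in 9.4.8, later events would count. The sponsor, the sites and the DMC could then keep different tallies under one rule. The ambiguity also reaches reporting, because SAP 7.8.1 plans a table of treatment-emergent DLTs without saying whether the window applies.

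**Working it through.** The documents give no figure for the share of treatment outside the window, so there is none to reproduce.

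**Full course.** Inputs: a 42-day window (5.4.2) and atezolizumab for up to 2 years, about 730 days (5.2).

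1 − 42/730 = 1 − 0.058 = 94.2%.

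The result stays between 94.1% and 94.3% whether the course is taken as 728 or 730.5 days and whether the window is 42 or 43 days.

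**Doses after Day 42** (protocol 7.1.1.3, 7.1.2.3 and Table 1), on nominal days:

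- LV305: Day 70, which is 1 of 4.
- G305: Days 56 and 84, plus six boosters (Days 126, 168, 210, 252, 294 and 336), which is 8 of 9.
- Atezolizumab: infusions every 21 days from Day 0 to Day 730 number 35. Those on Days 0, 21 and 42 fall by Day 42, leaving 32.

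**Expected treated time.** Few patients would complete two years. Assume that time on treatment is exponential with the design median PFS (3 and 5.2 months, protocol 10.3.1) and capped at 730 days. With L = ln 2 / (median × 30.4375):

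share after Day 42 = (e^(−42L) − e^(−730L)) / (1 − e^(−730L)).

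- Median 3 months: (0.727 − 0.004) / (1 − 0.004) = 0.726.
- Median 5.2 months: (0.832 − 0.041) / (1 − 0.041) = 0.825.

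The same curves give 6-month progression-free rates of 25.0% and 44.9%. These agree with the plan's 25% and 45%, and SAP section 4 states the exponential assumption for PFS.

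**What the window does to the rule.** One third of 12 is 4. Suppose, purely as an assumption, that a first qualifying event has constant hazard over 730 days, with two-year risk R, and that all 12 patients are followed throughout. The risk inside the window is 1 − (1 − R)^(42/730), and the number of patients with an event is binomial.

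| R | Risk by Day 42 | P(4 or more of 12), window only | P(4 or more of 12), whole course |
|---|---|---|---|
| 30% | 2.0% | 0.00007 | 0.51 |
| 50% | 3.9% | 0.0009 | 0.93 |
| 70% | 6.7% | 0.006 | 0.998 |

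The documents give no event rates. If toxicity clusters early, or patients stop early, the two right-hand columns move closer together.

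**Denominator.** Section 5.5 counts patients enrolled, without saying whether those still inside their 42 days are included. With assumed counts of 12 enrolled, 4 still in the window and 3 DLTs among the other 8, the rule reads 3/12 = 25%. Among patients fully observed it is 3/8 = 37.5%. One reading is below one third and the other above.

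**The case against.** The strongest reply is that late toxicity does not depend on these rules. Directly after its sentence on late events, the synopsis requires study drugs to be withheld for drug-related toxicity under Appendix F and for severe or life-threatening events, with no window. Section 5.4.3 and Appendix F govern atezolizumab at any time, and 6.3 requires discontinuation for intolerable toxicity. Many late events also reach the DMC promptly. Related serious events and MEOIs go to the sponsor and DMC (5.1), MEOIs are reported within 24 hours (9.4.8), and 5.8 lets DMC review modify or stop the program.

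This largely disposes of the patient-level worry. A reader might infer that nothing in the trial responds to toxicity after Day 42. The documents do not support that. At study level, however, the remaining route is review at discretion, with no threshold stated.

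A second reply is that 5.4.2 says events in the window are DLTs without saying that only those are. A hepatic clause in 5.4.3 also names a DLT with no window. It is therefore too strong to say that a DLT can never arise later. But no other definition is offered, so the result is a rule with two readings, which is the defect.

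Third, 5.4.2 says that events attributed to atezolizumab do not automatically count toward the DLT stopping criteria, even inside the window. The 32 later infusions are therefore not all exposure that the window alone removes from the rule.

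Finally, the example in 7.2.2 of a patient with a tumor response and a DLT might be taken as proof that later DLTs were intended. It is not. The first on-study scan is at Day 42, within a week either way, and could show a response in a patient already suspended for a DLT inside the window.

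**Conclusion.** The contradiction stands, mainly at study level. As DLT is defined, the numerical suspension rule in 5.5 cannot count related Grade 3 or higher events after Day 42. The unwindowed one-third definition in 5.4.2 can, but it triggers nothing. The wording of 5.6 and 7.2.2 and the reporting period in 9.4.8 suggest that later events may have been intended, without settling it.

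The 94% is a ceiling that applies only to a patient treated for two full years. At the design medians, 73% to 82% of expected treated time lies after Day 42, if time on treatment follows the assumed PFS curve. The trigger probabilities only illustrate an assumed constant hazard. The rule does still work for the first 42 days of each newly enrolled patient.

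It would also go too far to call 5.5 the trial's only numerical toxicity rule after the run-in. It is the study-level suspension rule that the protocol and SAP state, but monitoring detail is deferred to a DMC charter that is not among the documents.

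**What to change.** Reconcile protocol 5.4.2, 5.5, 5.6, 7.2.2 and the synopsis with SAP 3.1. Each rule should name the event it uses: either the 42-day DLT or the unwindowed related Grade 3 or higher event already in the first paragraph of 5.4.2. If both are kept, give them different names, and carry those names into the DLT table in SAP 7.8.1 and into the DMC charter.

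In 5.5, also state whether patients still inside the 42-day window count in the denominator. The evaluability definition in 5.4.2 should not be carried over automatically. It is written for the run-in and tied to replacing patients, whereas 6.3 and 7.2.1 say that patients who discontinue or withdraw are not replaced. It also depends on completing the window, so it would not fit an unwindowed count.

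Which events and which patients count is for the sponsor and the DMC to decide. The cost is wording in the protocol, SAP and charter. No new data are needed, since grade, relatedness and onset are already collected. The downside is that the running count given to the DMC may be higher and a review may be triggered earlier.

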5.4.3 Toxicities Associated with Atezolizumab

Atezolizumab will be withheld until resolution (i.e., return to Grade 0-1) for the following event(s):

- Grade ≥ 2 pneumonitis
- Grade ≥ 3 symptomatic hepatic toxicities that do not resolve to Grade 2 within 48 hours or Grade ≥ 3 asymptomatic hepatic toxicities that do not resolve to Grade ≤ 1 within 3 weeks of onset with the following exceptions:
 - For patients with Grade 2 AST, ALT, alkaline phosphatase abnormality at baseline, an increase to $>8\times$ the upper limit of normal (ULN) that does not resolve to Grade 2 within 48 hours (if symptomatic) or Grade ≥ 3 asymptomatic hepatic toxicities that do not resolve to Grade ≤ 1 within 3 weeks of onset (if asymptomatic) will be considered a DLT.
- Grade ≥ 2 diarrhea or colitis
- Symptomatic hypothyroidism, hyperthyroidism, pan hypopituitarism, or any Grade ≥ 3 endocrine events
- Grade ≥ 3 ocular events
- Grade ≥ 3 dermatologic events
- Grade ≥ 2 neuropathy
- Grade ≥ 4 neutropenia (absolute neutrophil count [ANC] $<500/\mu\text{L}$) lasting ≥ 7 days, thrombocytopenia, anemia, or Grade ≥ 3 febrile neutropenia
- Grade ≥ 3 non-hematologic, non-hepatic organ toxicity, excluding the following:
 - Grade 3 immune related AE (irAE) that resolves to Grade ≤ 1 within 3 weeks of its onset (may include events that resolve after medical treatment, including immunosuppressant therapy)
 - Grade 3 nausea or vomiting that resolves to Grade ≤ 1 within 72 hours of appropriate supportive therapy
 - Grade ≥ 3 fatigue that resolves to Grade ≤ 2 within 7 days
 - Grade 3 arthralgia that can be adequately managed with supportive care or that resolves to Grade ≤ 2 within 7 days

- Grade 3 fever (in the absence of any clinically significant source of fever) that resolves to Grade ≤ 2 within 7 days with supportive care
- Grade ≥ 3 laboratory abnormality that is asymptomatic and deemed by the Investigator not to be clinically significant
- Grade 3 tumor flare defined as local pain, irritation, or rash localized at sites of known or suspected tumor
- Grade 3 infusion reaction that resolves within 6 hours to Grade ≤ 1

These reactions, along with any DLTs, will be reviewed by the DMC on a case-by-case basis and may be considered DLTs if they meet the criteria outlined above. Atezolizumab treatment can be resumed in patients whose adverse reactions recover to Grade 0-1.

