7.2 Treatment Administration

For patients randomized to the combination treatment arm, the dosing regimens for LV305 and G305 will mimic those used in previous Phase 1 studies. The dose of each agent will be given according to the schedules outlined in [Table 1](#) (combination dosing arm with atezolizumab) or [Table 2](#) (control arm).

Two doses of LV305 will be administered 2 weeks apart on Weeks 0 and 2, which will be followed every 2 weeks with G305 alternating with LV305 ([Figure 1A](#)). The alternating regimen that will be used was designed primarily to maximize the induction of CD8 T-effector/memory cells by LV305 and then expand or boost them with the G305. Nonclinical studies suggest that injections every 2–4 weeks generate the most durable and highest magnitude immune responses^{6,20} and that the responses continue to be boosted with additional treatments.

Patients will be given an IV infusion of 1200 mg atezolizumab over 30 to 60 minutes every 3 weeks starting on Day 0 until disease progression or unacceptable toxicity ([Figure 1A&B](#)). The initial dose of atezolizumab will be delivered over 60 (± 15) minutes. If the first infusion is

tolerated without infusion-associated AEs, the second infusion may be delivered over 30 (\pm 10) minutes. If the 30-minute infusion is well tolerated, all subsequent infusions may be delivered over 30 (\pm 10) minutes. For the first infusion, the patient's vital signs (HR, respiratory rate, BP, and temperature) should be measured within 15 minutes of the infusion, during the 60-minute infusions (every 15 [\pm 5] minutes), and 30 minutes after the infusion. For subsequent infusions, vital signs do not need to be obtained during the infusion if the prior infusion was tolerated without symptoms. The management of any infusion-related reactions are outlined in [Section 7.4.4.1](#).

Patients in both study arms will be treated with atezolizumab therapy alone every 3 weeks starting at from Day 0 until disease progression or unacceptable toxicity. Due to administrative reasons, atezolizumab treatment may be administered up to 3 days before or after the scheduled dosing day.

Any overdose or incorrect administration of study drug should be noted on the Study Drug Administration electronic Case Report Form (eCRF). AEs associated with an overdose or incorrect administration of study drug should be recorded on the Adverse Event eCRF. Further details are provided in [Section 9.4.1](#).

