7.4.4.1 Infusion-related Reactions

Symptoms that occur during or within 24 hours after an infusion of atezolizumab may be part of an acute infusion reaction. The non-serious symptoms should be recorded as separate AEs on the AE eCRF. Serious symptoms should be reported as one SAE with the most medically significant sign or symptom as the primary event term. Additional signs and symptoms should be reported in the 'Additional Case Details' section of the AE eCRF page.

Infusion-related reactions will be managed according to severity according to the following procedures:

- In the event that a patient experiences a mild infusion-related event (National Cancer Institute Common Toxicity Criteria for Adverse Events [NCI CTCAE] Grade 1), the infusion rate should be reduced to half the rate being given at the time of event onset. Once the event has resolved, the Investigator should wait 30 minutes while delivering the infusion at the reduced rate. If tolerated, the infusion rate may then be increased to the original rate.
- In the event that a patient experiences a moderate infusion-related event (NCI CTCAE Grade 2) or flushing, fever, or throat pain, the patient should have his or her infusion immediately interrupted and should receive aggressive symptomatic treatment. The infusion should be restarted only after the symptoms have adequately resolved to baseline grade. The infusion rate at restart should be half the infusion rate that was in progress at the time of the onset of the infusion-related event.
- For severe or life-threatening infusion-related events (NCI CTCAE Grade 3 or 4), the infusion should be stopped immediately, and aggressive resuscitation and supportive measures should be initiated. Patients experiencing severe or life-threatening infusion-related events will not receive further infusion and will be further managed as clinically indicated until the event resolves.

Further details regarding the management of Infusion-related reactions are provided in [Appendix F](#).

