Hepatitis	In patients receiving atezolizumab as a single agent, hepatitis and elevations of alkaline phosphatase, AST and ALT have been reported in 0.5%, 4.1%, 6.1% and 5.6% of patients, respectively. In the clinical program, <1% of patients experienced serious adverse events of hepatobiliary disorders including autoimmune hepatitis (5), hepatitis (3), and the following (1 patient each): drug induced liver injury, hepatic failure, abnormal hepatic function, hepatocellular injury, and liver disorder.
Hypersensitivity	Hypersensitivity reactions including allergic and anaphylactic reactions have been reported in <1% of patients receiving single agent. Outcomes for these events were considered resolved. Patients may present with complaints such as flushing, fever, chills, blood pressure change, tachycardia or shortness of breath
Influenza-like illness	Influenza like illness has been reported in patients receiving atezolizumab as a single agent in PCD4989g (7.3%). Events associated with influenza like illness were primarily observed one to two weeks after receiving the first cycle. Reactions have included fever, fatigue, asthenia, chills, myalgia, arthralgia and headache. The events have been mild to moderate in severity.

Identified Risk	Description of Risk
Infusion-related reactions	Symptoms may present within 30 minutes to 24 hours after infusion, are generally mild and manageable, and wane with subsequent infusions. With single agent atezolizumab, IRRs have been reported in 0.4% of patients. The most common symptoms reported with single agent use within 24 hours of the first cycle were pyrexia, fatigue, nausea, hypertension, headache and diarrhea.
Neurologic disorders	Myasthenia gravis and Guillain-Barré syndrome have been observed in less than 1% of patients taking atezolizumab. Patients may present with signs and symptoms of sensory and/or motor neuropathy. Meningitis (non-infectious) has also been reported in <1% of patients. Patients with meningitis may present with altered mental status, confusion, headache, or fever. Diagnostic work-up is essential for an accurate characterization to differentiate between alternate etiologies.

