Appendix Table 11 Management Guidelines for Infusion-Related Reactions

Infusion Reactions	Severity	Management
	Grade 1	
 • Reduce infusion rate to half the rate being given at the time of event onset. • After the event has resolved, the investigator should wait for 30 minutes while delivering the infusion at the reduced rate • If tolerated, the infusion rate may then be increased to original rate
	Grade 2	
 • Interrupt atezolizumab infusion • Administer aggressive symptomatic treatment. • Restart only after the symptoms have adequately resolved to baseline grade • The infusion rate at restart should be half of the infusion rate that was in progress at the time of the onset of the IRR • At next cycle, administer oral premedication with antihistamine and anti-pyretic and monitor closely for infusion reaction
	Grades 3 - 4	
 • Stop infusion • Proper medical management which may include oral or IV antihistamine, anti-pyretic, glucocorticoids, epinephrine, bronchodilators, and oxygen • Discontinue atezolizumab • Contact the Medical Monitor, if atezolizumab is discontinued.

IRR = infusion-related reactions.

Pancreatic Events

Symptoms of abdominal pain associated with elevations of amylase and lipase, suggestive of pancreatitis, have been associated with the administration of other immuno-modulatory agents. The differential diagnosis of acute abdominal pain should include pancreatitis. Appropriate work-up should include an evaluation for obstruction, as well as serum amylase and lipase tests.

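### Section 5.4.3 and the synopsis let atezolizumab continue after a Grade 3 infusion reaction that resolves within 6 hours; Section 7.4.4.1 and Appendix Table 11 end it after any Grade 3-4 reaction.

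*Protocol*

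**What the plan says.** Two sets of instructions cover a severe infusion reaction to atezolizumab.

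**The withholding list.** Protocol Section 5.4.3 opens with an instruction to withhold atezolizumab until return to Grade 0-1 for the events it lists. One of these is non-hematologic, non-hepatic organ toxicity of Grade 3 or higher, followed by exclusions. The last exclusion is a "Grade 3 infusion reaction that resolves within 6 hours to Grade" 1 or lower. The section ends: "Atezolizumab treatment can be resumed in patients whose adverse reactions recover to Grade 0-1". The synopsis row on toxicities associated with atezolizumab carries the same exclusion and the same closing sentence.

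**The infusion-reaction rules.** Section 7.4.4.1 grades the response to infusion reactions. For severe or life-threatening events, which it defines as CTCAE Grade 3 or 4, it says: "Patients experiencing severe or life-threatening infusion-related events will not receive further infusion". In Appendix Table 11, the Grades 3-4 row lists stopping the infusion and, as a separate item, "Discontinue atezolizumab".

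**Cross-references.** Section 7.2 states: "The management of any infusion-related reactions are outlined in" Section 7.4.4.1. Section 7.2.2 says that "study treatment must be withheld for AEs or infusions reactions associated with atezolizumab treatment as outlined in" Appendix F. The Safety Monitoring row of the synopsis says: "The study drugs must be withheld for drug-related toxicities as outlined in Appendix F".

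**The concern.** The two sets of rules give opposite answers for one event: a Grade 3 infusion reaction that settles to Grade 1 or lower within 6 hours. Section 5.4.3 and the synopsis do not withhold the drug and permit resumption. Section 7.4.4.1 and Appendix Table 11 end it.

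The likely origin is a list of exceptions meant to define dose-limiting toxicity that was placed under a heading about withholding drug. Section 5.4.2 does point to 5.4.3 when it discusses which atezolizumab events count as DLTs. As written, though, the list governs dosing.

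Patient safety is at stake, and the error runs in the unsafe direction, towards re-exposure after a severe infusion reaction. The dosing conflict applies in both arms, because both receive atezolizumab every 3 weeks for up to 2 years at up to 20 sites. DLTs are assessed only in the combination arm.

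**Working it through.** **Step 1. The rules side by side for a Grade 3 infusion reaction resolving to Grade 1 or lower within 6 hours**

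| Place | Withhold? | Further atezolizumab? |
|---|---|---|
| Section 5.4.3 | No, excluded by name | Yes, resumption allowed at Grade 0-1 |
| Synopsis, atezolizumab toxicities | No, excluded by name | Yes, same sentence |
| Section 7.4.4.1 | Infusion stopped at once | No further infusion |
| Appendix Table 11, Grades 3-4 | Infusion stopped | Atezolizumab discontinued |

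**Step 2. Can the second pair mean only the current infusion?** The sentence in 7.4.4.1 goes on to speak of further management until the event resolves, so this reading has to be considered. Three points weigh against it:

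- The time limit attaches most naturally to the clinical management, not to the ban on infusion.
- Appendix Table 11 lists stopping the infusion and discontinuing the drug as separate actions.
- Both places give restart steps for Grades 1 and 2 and none for Grades 3-4.

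Ending the drug is the natural reading.

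**Step 3. Is there a precedence rule?** Sections 7.2 and 7.2.2 and the synopsis Safety Monitoring row point to 7.4.4.1 or Appendix F. None says that these override 5.4.3, and the last two speak of withholding, not of ending treatment.

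**Step 4. How often could it arise?** Appendix Table 3 states: "With single agent atezolizumab, IRRs have been reported in 0.4% of patients". The plan gives no rate by grade or by time to resolution, so only the any-grade frequency can be worked out.

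- Among 80 patients: 0.004 × 80 = 0.32 expected; chance of at least one = 1 − 0.996^80 = 0.274.
- Per arm of 40: 0.004 × 40 = 0.16 expected; chance of at least one = 1 − 0.996^40 = 0.148.

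For the uncertainty, assume the 0.4% comes from the 558 single-agent patients in the table note. Then it is 2 patients: 2/558 = 0.36%, which rounds to 0.4%, while 1/558 = 0.18% and 3/558 = 0.54% do not. The Clopper-Pearson 95% interval for 2/558 is 0.043% to 1.29%. Multiplied by 80, this is 0.03 to 1.03 patients with a reaction of any grade.

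**The case against.** The strongest reply is that the protocol already leads the site to the stricter rule. Section 5.6 sends the reader to 7.2.2 for dose modifications, 7.2.2 sends infusion reactions to Appendix F, 7.4.4 does the same, and 7.2 points to 7.4.4.1. No pointer on managing infusion reactions leads to 5.4.3, and specific graded text would ordinarily govern over a sub-bullet in a general list. This shows which rule was probably intended. It does not settle the matter for a site working from 5.4.3 or the synopsis, because no precedence is stated.

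It can also be said that leaving an event off a withholding list is not an instruction to re-dose, and that the resumption sentence concerns events for which drug was withheld. But Section 7.2 schedules atezolizumab every 3 weeks, so if nothing withholds it, the next dose is due.

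There are real safeguards. Section 9.4.8 includes events suggestive of an infusion reaction syndrome among the medical events of interest, which must be reported to the sponsor within 24 hours, and requires assessment for such events before each dose. Section 5.4.3 provides for case-by-case DMC review. With about three weeks between doses, the sponsor should usually know before the next one. This lowers the risk but does not correct the rule.

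Two further points stand. Appendix Table 11 says discontinue, whereas several other Appendix F tables say permanently discontinue, so the stricter side could be firmer. And the frequencies above are for reactions of any grade, which Appendix Table 3 describes as generally mild, so they overstate how often the disputed event should occur.

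**Conclusion.** The concern holds. For a Grade 3 infusion reaction that resolves within 6 hours, the current protocol gives incompatible dosing instructions in two pairs of places, and the more permissive pair is the less safe one. The cross-references suggest that Appendix F was meant to govern, but the protocol does not say so.

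The practical size is small: about 0.32 infusion reactions of any grade among 80 patients at the quoted rate, or 0.03 to 1.0 if that rate is 2 of 558. The disputed reactions are an unquantified subset. Both figures rest on single-agent data. In the combination arm, LV305 or G305 is given on the same day as atezolizumab on Days 0, 42 and 84, and the documents give no infusion-reaction rate for that combination. No sample size, error rate or endpoint analysis changes.

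The wording should be corrected because it is an operative safety rule, even though the event is expected to be rare.

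**What to change.** In Section 5.4.3 and the matching synopsis row:

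1. Say that the exclusion of a rapidly resolving Grade 3 infusion reaction applies only to whether the event is classed as a DLT.
2. Add that dosing after any Grade 3-4 infusion reaction follows Section 7.4.4.1 and Appendix Table 11, with no further atezolizumab, notwithstanding the sentence that allows resumption at Grade 0-1.

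A useful extension is one sentence stating that Appendix F prevails over 5.4.3 wherever they differ. The same tension exists for Grade 3-4 pneumonitis (Appendix Table 6), hepatic (Table 7), endocrine (Table 9) and ocular (Table 10) events, where Appendix F discontinues the drug but 5.4.3 would withhold and resume it. Without that sentence, a clause confined to infusion reactions could be taken to mean that 5.4.3 governs the others.

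The cost is protocol wording in two places, with no new data, procedures or analyses. Under Section 16.1 it still needs an amendment, submitted to the FDA and approved by the IRB.
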